## **8.2 Recording/Reporting requirements**

### **8.2.1 Eliciting adverse event information**

Throughout the duration of the study subjects will be monitored for adverse events. At each study visit (weeks 1, 2, 3, 4, 6 and 6 months) and follow-up phone call (3, 4, 9 and 12 months), subjects will be asked to provide any information about possible adverse events that may have occurred since the last visit. Subjects will be asked to provide information about any reaction to the study medication, any new health-related symptoms they may be experiencing, and any new events or injury that may impact their compliance with the study protocol. If during the follow-up phone call the subject reports a new or ongoing adverse event, a follow-up clinic visit will be scheduled.

### **8.2.2 Recording requirements**

All observed or volunteered adverse events (serious or non-serious) and abnormal test findings, regardless of study group or suspected causal relationship to the study drug(s) will be recorded in the subjects' case histories. For all adverse events, sufficient information will be pursued and/or obtained so as to permit 1) an adequate determination of the outcome of the event (i.e., whether the event should be classified as a *serious adverse event*) and; 2) an assessment of the causal relationship between the adverse event and the study drug(s).

Adverse events or abnormal test findings felt to be associated with the study drug(s) will be followed until the event (or its sequelae) or the abnormal test finding resolves or stabilizes at a level acceptable to the Sponsor-Investigator.

#### **8.2.2.1 Abnormal test findings**

An abnormal test finding will be classified as an *adverse event* if one or more of the following criteria are met:

- The test finding is accompanied by clinical symptoms.
- The test finding necessitates additional diagnostic evaluation(s) or medical/surgical intervention; including significant additional concomitant drug treatment or other therapy.
  - Note: simply repeating a test finding, in the absence of any of the other listed criteria, does not constitute an adverse event.

- The test finding leads to a change in study drug dosing or discontinuation of subject participation in the clinical research study.
- The test finding is considered an adverse event by the Sponsor-Investigator of the IND application.

### **8.2.2.2 Causality and severity assessment**

The Sponsor-Investigator of the IND application will promptly review documented adverse events and abnormal test findings to determine: 1) if the abnormal test finding should be classified as an adverse event; 2) if there is a reasonable possibility that the adverse event was caused by the study drug(s); and 3) if the adverse event meets the criteria for a *serious adverse event*.

If the Sponsor-Investigator's final determination of causality is "unknown and of questionable relationship to the study drug(s)", the adverse event will be classified as *associated with the use of the study drug(s)* for reporting purposes. If the Sponsor-Investigator's final determination of causality is "unknown but not related to the study drug(s)", this determination and the rationale for the determination will be documented in the respective subject's case history.

## **8.3 Reporting of adverse reactions**

### **8.3.1 Reporting of adverse reactions to the FDA**

#### **8.3.1.1 Written IND Safety Reports**

The Sponsor-Investigator will submit a written IND Safety Report (i.e., completed FDA Form 3500 A) to the responsible new drug review division of the FDA for any observed or volunteered adverse event that is determined to be a *serious and unexpected, suspected adverse reaction*. Each IND Safety Report will be prominently labeled, "IND Safety Report", and a copy will be provided to all participating investigators (if applicable) and sub-investigators.

Written IND Safety Reports will be submitted to the FDA as soon as possible and, in no event, later than 15 calendar days following the

Sponsor-Investigator's receipt of the respective adverse event information and determination that it meets the respective criteria for reporting.

For each written IND Safety Report, the Sponsor-Investigator will identify all previously submitted IND Safety Reports that addressed a similar suspected adverse reaction experience and will provide an analysis of the significance of newly reported, suspected adverse reaction in light of the previous, similar report(s) or any other relevant information.

Relevant follow-up information to an IND Safety Report will be submitted to the applicable review division of the FDA as soon as the information is available and will be identified as such (i.e., "Follow-up IND Safety Report").

If the results of the Sponsor-Investigator's follow-up investigation show that an adverse event that was initially determined to not require a written IND Safety Report does, in fact, meet the requirements for reporting; the Sponsor-Investigator will submit a written IND Safety Report as soon as possible, but in no event later than 15 calendar days, after the determination was made.

### **8.3.1.2 Telephoned IND Safety Reports – Fatal or life-threatening suspected adverse reactions**

In addition to the subsequent submission of a written IND Safety Report (i.e., completed FDA Form 3500A), the Sponsor-Investigator will notify the responsible review division of the FDA by telephone or facsimile transmission of any *unexpected, fatal or life-threatening suspected adverse reaction*.

The telephone or facsimile transmission of applicable IND Safety Reports will be made as soon as possible but in no event later than 7 calendar days after the Sponsor-Investigator's receipt of the respective adverse event information and determination that it meets the respective criteria for reporting.

### **8.3.2 Reporting adverse events to the responsible IRB**

In accordance with applicable policies of the University of Pittsburgh Institutional Review Board (IRB), the Sponsor-Investigator will report, to the IRB, any observed or volunteered adverse event that is determined to be: 1) *associated with the investigational drug or study treatment(s)*; 2) *serious*; and 3) *unexpected*. Adverse event reports will be submitted to the IRB in accordance with the respective IRB procedures.

Applicable adverse events will be reported to the IRB as soon as possible and, in no event, later than 10 calendar days following the sponsor-investigator's receipt of the respective information. Adverse events which are: 1) *associated with the investigational drug or study treatment(s)*; 2) *fatal or life-threatening*; and 3) *unexpected* will be reported to the IRB within 24 hours of the Sponsor-Investigator's receipt of the respective information.

Follow-up information to a reported adverse event will be submitted to the IRB as soon as the relevant information becomes available. If the results of the Sponsor-Investigator's follow-up investigation show that an adverse event that was initially determined to not require reporting to the IRB does, in fact, meet the requirements for reporting; the Sponsor-Investigator will report the adverse event to the IRB as soon as possible, but in no event later than 10 calendar days, after the determination was made.

#### **8.4 Withdrawal of subjects due to adverse events**

Vital signs, including blood pressure and heart rate will be monitored daily prior to each rehabilitation session. Individuals with symptomatic hypotension (defined as symptoms consistent with hypotension including dizziness, lightheadedness etc. with systolic or diastolic blood pressure less than 90 and 60 mm Hg respectively) will be discontinued from the study. Withdrawal of a subject due to symptomatic hypotension will be reported as an adverse event.

Blood work, including a chemistry panel with electrolytes and complete blood cell count (CBC) will be performed prior to randomization and at 2, 4, and 6 weeks after randomization. The blood work will be used to assess hemoglobin and hematocrit counts, serum potassium and uric acid levels, liver function (alanine aminotransferase (ALT), aspartate aminotransferase (AST) and alkaline phosphatase), renal function (blood urea nitrogen [BUN] and serum creatinine), creatine phosphokinase (CPK) to assess muscle injury, and pregnancy in women (human chorionic gonadotropin (hCG)). Additional blood work will be ordered if subjects report new fatigue, peripheral edema or urinary symptoms. Follow-up blood work will be performed 4-6 weeks ( $\pm 3$  days) after discontinuing medication to ensure that lab values have returned to normal ranges after discontinuation of the study medication. Abnormal lab values resulting in subject withdrawal from the study will be reported as an adverse event.

Human chorionic gonadotropin (hCG) be determined to identify pregnant women will be assessed prior to randomization and at 2, 4 and 6 weeks after randomization. Women that are pregnant prior to randomization will be discontinued from the study, but will not be reported as an adverse event.

Human chorionic gonadotropin will also be determined for females enrolled in the study who expect that they For females enrolled in the study that have become pregnant, the study medication will be stopped immediately and the subject will be withdrawn from the study. Pregnancy necessitating withdrawal from the study will be reported as an adverse event.

Adverse events or abnormal test findings felt to be associated with the study drug(s) will be followed until the event (or its sequelae) or the abnormal test finding resolves or stabilizes at a level acceptable to the Sponsor-Investigator.

The severity of an adverse event will be determined by the study medical director based on the criteria stated in section 8.1. Additionally, the medical director will assign the event a grade of mild, moderate, or severe. If it becomes medically necessary to withdraw the subject from the study, the study medication will be discontinued. The subject will be followed clinically until the adverse event or abnormal test findings felt to be associated with the study drug resolves or stabilizes at a level acceptable to the Sponsor-Investigator. This follow-up will include assessment of vital signs, physical examination and assessment of blood work. Follow-up blood work will be performed 4-6 weeks ( $\pm 3$  days) after discontinuing medication to ensure that lab values have returned to normal ranges after discontinuation of the study medication. The subject will be treated for any medication related problems as clinically appropriate. Information from this appointment will be documented in the subject's case file. The patient will be terminated from the study, and will not complete any further follow-up appointments for the study. Subjects that are terminated from participation in the study due to an adverse event will be replaced by recruitment of another subject.

## 9.

## **Statistical Methods/Data Analysis:**

### **9.1 Study endpoints**

#### **9.1.1 Primary endpoint(s)**

**Specific Aim #1: To determine safety and tolerability of Losartan when used for treatment of an acute grade II or III hamstring strain.**

To assess safety, vital signs will be monitored daily and we will also monitor the frequency of abnormal lab values as well as adverse and serious adverse events during period of active intervention as well as throughout the subjects' participation in the study. To assess the side effect profile of Losartan in this population, we will monitor the frequency of subject complaints, symptoms (dizziness, new fatigue, peripheral edema, urinary symptoms) and laboratory measures of liver and renal function, haemoglobin and haematocrit counts and serum potassium and uric acid levels. The frequency of abnormal lab values, adverse and serious adverse events and side effects will be monitored separately for the Losartan and placebo control groups.

**Specific Aim #2: Recovery of Hamstring Muscle Function and Structure**

The primary endpoints to assess hamstring muscle function are the injured to contra-lateral leg differences in the popliteal angle at 6 weeks and 6 months and the injured to contra-lateral ratio of peak isokinetic hamstring torque at 6 weeks and 6 months.

The primary endpoint to assess hamstring structure will be the length and volume of fibrosis within the hamstrings at 6 months as evidence on 3 Tesla MRI.

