Recently, we performed a preliminary phase 1 case study involving two adult males with acute/recurrent hamstring muscle injury. In both patients, we initiated treatment with Losartan after the acute period of necrosis/degeneration and inflammation. Both patients demonstrated normal hamstring flexibility and strength recovery by 6-9 weeks after injury. To date (> 2 years after treatment) neither individual has suffered any re-injury to their hamstring muscles, which may represent the most important feature of the study. Furthermore, both individuals tolerated the Losartan with no reported side effects and remained normotensive throughout the 30 day course of treatment. Despite the limitations of making treatment decisions based on two case reports, we are encouraged by the results of these interventions.

Based on our basic science results and preliminary clinical experience, we hypothesize that subjects who receive Losartan for a short duration along with the current standard of care treatment after sustaining an acute grade II or III

hamstring muscle injury will have less formation of fibrosis and a faster return to their prior level of activity and muscle function when compared to a placebo control group who only receives the current standard of care treatment. To test this hypothesis we propose a phase 1 randomized double blind placebo-controlled clinical trial to compare the use of Losartan (50mg/day) to placebo in 20 individuals with an acute grade II or III hamstring injury between the ages of 18-35. The main goal of this study is to determine safety and tolerability and to provide pilot data to determine the magnitude of the effect and variability in the outcome of Losartan in comparison to placebo, which will allow a more accurate prediction of sample size for a future definitive clinical trial. Subjects enrolled in this study that are randomized to the active drug arm of the study will be given 50 mg of Losartan to be taken daily by mouth. This dose was chosen as it is the prescribed starting dose for the FDA-approved uses of losartan. It is also the dose prescribed for a case study of 2 patients with a severe hamstring strain that demonstrated improved muscle structure and function.

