#### **Specific Aim #2: To determine the effect of Losartan on recovery of hamstring muscle function and structure following an acute grade II or III hamstring strain.**

*Hypothesis 1.1:* Subjects who receive Losartan will have a quicker return of normal hamstring muscle function, as evidenced by better flexibility and strength of the hamstring muscle when compared to the control group who receives the current standard of care treatment without Losartan.

*Hypothesis 1.2:* Subjects who receive Losartan will have less formation of fibrosis compared to the control group who receives the current standard of care treatment without Losartan.

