**Table 1 – Summary of Study Procedures**

	Pre-treat	Day 0	1w	2w	3w	4w	6w	12w	4m	6m	9m	12m
Informed Consent	X											
Demographic Questionnaire	X											
Activity Level	X		X	X	X	X	X	X	X	X	X	X
Medical History	X											
Vital Signs ( standard and orthostatic blood pressure and heart rate)	X		X	X	X	X	X			X		
Physical Examination	X											
Blood Work	X			X		X	X					
Numerical Pain Rating Scale	X		X	X	X	X	X	X		X		
Hamstring flexibility	X		X	X	X	X	X			X		
Isometric hamstring strength testing	X		X	X	X	X	X			X		
Isokinetic hamstring strength testing							X			X		
3.0 Tesla MRI	X									X		
Randomization		X										
Day of 1 st Dose		X										
Medication Log Review			X	X	X	X						
Telephone follow-up									X	X	X	X
	Legend: pre-treat = pre-treatment; w = week; m = months											

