## **5. Study Drug(s):**

As described in section 1.2, losartan potassium is an FDA-approved drug for the treatment of hypertension, left ventricular hypertrophy and diabetic nephropathy. It is prescribed for oral intake at doses from 25-100 mg per day with a usual starting dose of 50 mg per day which is what will be used for this study. Losartan potassium was developed by Merck under the proprietary name Cozaar® and is now generically available.

Prior to starting the study medication, a study physician will review the effects of losartan, its side-effects and how the medication should be taken with all subjects. At this time, the physician will answer any questions the subject has regarding the study medication. Subjects will be evaluated weekly while they are taking the medication. Blood work will be repeated 2, 4 and 6 weeks after randomization to identify any clinically relevant abnormalities.

Following randomization, subjects will begin a closed label course of 50mg of Losartan daily for 4 weeks or placebo for the same duration of time. Losartan will be initiated within 7 days of injury after initial tests are performed and any abnormalities are ruled out. No initial dosage adjustment is necessary. The drug will be self-administered by the subject with or without food and will be ingested once a day. With the dose that will be used in this study, no tapering is necessary at the end of the intervention phase or if the subject needs to be withdrawn from the study.

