**Table 2 – Sets, Weight and Number of Repetitions for DAPRE Program**

Set	Portion of Working Weight Used	Number of Repetitions
1	50%	10
2	75%	6
3	100%	As many as possible
4	Adjusted based on number of repetitions in 3 rd set	As many as possible

Subjects will be permitted to begin high-speed running and agility drills when: 1) they have no palpable tenderness in the posterior thigh, 2) hamstring flexibility is within 3° of the un-injured leg and 3) resisted hamstring strength is 85% of the un-injured leg. Subjects will be permitted to return to full practice or military activity when they can tolerate high-speed running and agility drills for 3 consecutive days with no exacerbation of symptoms and when they can perform a 40-yard sprint with no posterior thigh tightness or twinges. Upon return to sports, subjects will be encouraged to continue with the rehabilitation program 3 days a week for at least 2 months after returning to sports.

To ensure consistency in the rehabilitation program for all subject, we will create educational training materials (video and written instructions) demonstrating the correct performance and progression of the rehabilitation program. This information will be distributed to all physical therapists and athletic trainers responsible for rehabilitation of the subjects participating in this study.

Compliance with the rehabilitation program will be assessed by reviewing the physical therapy or athletic training rehabilitation records. Additionally, subjects will independently track exercise compliance by recording the rehabilitation tasks that are performed on a daily basis in an exercise log. This log will be reviewed at each follow-up visit to ensure compliance with the rehabilitation program. To control for co-interventions, applications of heat and ultrasound and use of

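### Hypothesis 1.1 predicts faster recovery of flexibility and strength, but its primary endpoints are levels at 6 weeks and 6 months, and popliteal angle at weeks 1–4 enters no endpoint

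*Combined protocol and SAP*

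**What the plan says.** Section 2.1, Specific Aim #2, states Hypothesis 1.1 as "a quicker return of normal hamstring muscle function, as evidenced by better flexibility and strength of the hamstring muscle", compared with the control group.

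Section 9.1.1 gives two primary function endpoints for that aim. One is "the injured to contra-lateral leg differences in the popliteal angle at 6 weeks and 6 months". The other is isokinetic peak torque of the injured hamstrings relative to the uninjured side, at the same two times. Section 9.1.2 adds isometric strength, as a percentage of the other leg, at weeks 1, 2, 3, 4 and 6 and at 6 months, plus further isokinetic variables.

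Table 1 (section 3.1) schedules "Hamstring flexibility" before treatment, at weeks 1, 2, 3, 4 and 6, and at 6 months. Pain is rated on the same early visits and is described with the Aim 2 measures in section 6.4.2.2. Neither popliteal angle before week 6 nor pain at any time appears in 9.1.1 or 9.1.2.

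Section 9.4 sends repeatedly measured outcomes to mixed models. Age, sex and treatment group are given as examples of fixed effects, and subject and site are random effects. No outcome is named, and neither is a term for visit.

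Section 1.2 reports on two losartan-treated cases: "Both patients demonstrated normal hamstring flexibility and strength recovery by 6-9 weeks after injury".

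**The concern.** A hypothesis about speed needs a quantity that changes with speed. A level at a fixed time does so only while the arms are still recovering. Once both are close to normal, the difference in level vanishes however much sooner one arm got there.

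Section 9.2 says the trial cannot detect differences and exists to describe trends and supply effect sizes for later trials. If the reported effect on flexibility is taken when much of the contrast has passed, the next trial is planned on a number that understates, or at 6 months hardly reflects, what Hypothesis 1.1 predicts. If the weekly readings have no planned role, any later use of them is a choice among visits made with the data in view.

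**Working it through.** **1. Timing.** Section 5 states "Losartan will be initiated within 7 days of injury", so the 6-week visit falls about 6 to 7 weeks after injury. That is the start of the 6–9 week window in the two cases. Six months is far beyond it. Isokinetic torque has no pre-treatment measurement, so it cannot trace early recovery.

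**2. How much contrast each time point keeps.** The documents give no recovery curve, deficit or SD, so everything in this step is assumed. Let the remaining fraction of the deficit be f(t,T) = exp(ln(0.05)·t/T), which is 95% recovered at T weeks. The between-arm gap is f(t,T_control) − f(t,T_losartan). For 9 v 6 weeks the gap is 0.110, 0.146, 0.145, 0.128 and 0.086 at weeks 1, 2, 3, 4 and 6, with a peak of 0.148 at week 2.4. Week 6 therefore keeps 0.0857/0.148 = 58%.

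| T control / losartan (weeks) | Peak at week | Week 6 as share of peak | 6 months as share of peak |
|---|---|---|---|
| 6 / 4 | 1.6 | 26% | 0% |
| 7.5 / 6 | 2.2 | 50% | <0.1% |
| 9 / 6 | 2.4 | 58% | 0.1% |
| 12 / 8 | 3.3 | 80% | 1.0% |
| 12 / 9 | 3.5 | 83% | 1.3% |
| 18 / 12 | 4.9 | 98% | 7.9% |

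**3. What averaging over weeks 1–6 would gain.** Assume equal variance at each visit and a common within-subject correlation ρ. The SD of a five-visit mean relative to one visit is √((1+4ρ)/5). The ratio of standardised effects is (mean gap / that SD) / gap at week 6. For 9 v 6 weeks and ρ = 0.5, the mean gap is 0.6143/5 = 0.1229 and the SD factor is √(3/5) = 0.775, so the ratio is (0.1229/0.775)/0.0857 = 1.85. Over ρ = 0.3 to 0.7 the ratio is 1.6–4.1 in the three faster scenarios and 0.95–1.6 in the three slower ones.

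**4. The same in degrees.** Take deficit(t) = D·2^(−t/h), with D the starting side difference and h the half-life in days. Time to within 3° is h·log2(D/3).
- D = 20°, h = 14 v 10: 38.3 v 27.4 days, about 11 days sooner. The gap is 2.42° at week 2, 2.41° at week 3, 1.41° at week 6 (2.5° v 1.1° remaining) and 0.00° at 6 months. Week 6 keeps 1.41/2.42 = 58% of the largest gap at a scheduled visit.
- D = 15, 20, 25°, h = 12 v 9: 7.0, 8.2 and 9.2 days sooner; 0.74°, 0.98° and 1.23° at week 6.
- D = 25°, h = 14 v 10: 12.2 days sooner; 1.76° at week 6.

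**5. Sample size.** Section 9.2 gives no alpha, effect size or SD, so the figure of 20 cannot be reproduced. With 10 per arm and an assumed two-sided 0.05, the standardised difference detectable with 80% power is (1.96+0.84)·√(2/10) = 1.25. Power is 20% at 0.5 and 43% at 0.8. This agrees with the plan's own statement, so the point concerns which quantity is estimated.

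**The case against.** A reader might infer that both primary time points fall after recovery is complete, so that the trial would return an effect near zero. The documents support that only for 6 months. The evidence for week 6 is two treated cases without controls, and under the trial's hypothesis placebo subjects recover later. In the scenarios where the losartan arm itself takes 6 to 9 weeks, week 6 keeps 50–83% of the peak gap. The illustration also lets the arms diverge from the first dose; a delayed effect would favour week 6 further.

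A reader might also infer that the plan measures speed nowhere. It does. Isometric strength is a weekly secondary endpoint, and Aim 3's primary outcome is days from injury to full practice. The rehabilitation steps in section 6.4.1 make "hamstring flexibility is within 3° of the un-injured leg" one condition for high-speed running, so early flexibility feeds indirectly into that outcome. But Aim 3 tests Hypothesis 3 and also depends on tenderness, running drills and a sprint. It gives no estimate for flexibility itself.

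Section 9.4 could take in weekly popliteal angle, and its list of fixed effects is open. That objection stands in part: the data are not excluded. But a single treatment coefficient averages over whichever visits are entered, which is not stated, and without visit terms it does not describe recovery over time.

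Pain is not part of Hypothesis 1.1, which names flexibility and strength. Its absence from the endpoint lists is an omission, not a mismatch with the hypothesis.

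**Conclusion.** The mismatch stands on the text. Hypothesis 1.1 predicts "Subjects who receive Losartan will have a quicker return of normal hamstring muscle function"; its primary endpoints are levels at two late times, weekly popliteal angle is assigned to no endpoint, and the planned model as written does not estimate speed of flexibility recovery.

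The 6-month value says almost nothing about speed (at most 8% of the peak gap in every scenario tried). The 6-week value may capture only part of the effect: about 26–58% if control recovery takes 6–9 weeks, 80–98% if it takes 12–18 weeks. These percentages rest on an assumed exponential recovery and assumed recovery times. The finding that 6 months is uninformative about speed is robust across them; the loss at week 6 is not. This should be fixed because effect-size estimation is the trial's stated purpose, but it does not invalidate the existing endpoints.

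**What to change.** In section 9, for Hypothesis 1.1:

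- **Add** the between-arm difference in mean popliteal-angle side difference over weeks 1, 2, 3, 4 and 6, adjusted for the pre-treatment value and reported with a confidence interval. Estimate it from the section 9.4 mixed model with visit and treatment-by-visit terms stated.
- **Report** the isometric strength ratio in the same way.
- **Optional, secondary and descriptive:** time to a pre-stated side-to-side threshold, treated as interval-censored between visits. State which isometric test angle is used (section 6.4.2.2 tests 30° and 90°, and the 85% strength criterion in section 6.4.1 does not name its test). Require the threshold to be sustained, because with the cited inter-observer ICC of .72 for popliteal angle a single reading may cross it by chance. Such a threshold is for analysis only and changes no rehabilitation rule.
- **List** pain at weeks 1–6 as secondary, for completeness.
- **Keep** the 6-week and 6-month endpoints.

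The cost is wording and one or two more descriptive endpoints in a 20-subject pilot. Every reading is already scheduled. If recovery proves slow, the weekly mean gains little over week 6 (ratio 0.95 at worst in the scenarios above), which is a reason to report both. The change should be made before unblinding.
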